2.6. STUDY ENDPOINTS

2.6.1. PRIMARY EFFICACY ENDPOINT:

- Change from baseline in MADRS total score at Week 6.

Document:

Author:

Version Number:

V2.0

Version Date:

21MAY2020

Template No: CS_TP_BS016 Revision 4
Effective Date: 01Apr2016

Reference: CS_WI_BS005

2.6.2. SECONDARY EFFICACY ENDPOINT:

- Change from baseline in global severity assessed by the CGI-BP-S score (depression) at Week 6.

2.6.3. PHARMACOKINETIC ENDPOINTS:

- Plasma concentrations of R-amisulpride and S-amisulpride.
- Plasma concentrations of prolactin.

2.6.4. OTHER ENDPOINTS:

- Number and percentage of treatment responders, defined as $\geq 50\%$ reduction from baseline in MADRS total score at Week 6.
- Time to treatment response, defined as $\geq 50\%$ reduction from baseline MADRS total score.
- Change from baseline in anxiety symptoms based on the HAM-A total score at Week 6.
- Incidence of symptom remission, defined as a MADRS total score of ≤ 12 at Week 6.
- Time to remission, defined as MADRS total score of ≤ 12 .
- Functional impairment assessed by change from baseline in the SDS total score at Week 6.
- Subject self-report of overall depressive symptom severity, assessed by change from baseline in the QIDS-SR16 total score at Week 6.

2.6.5. SAFETY ENDPOINTS:

- Incidence of treatment-emergent mania, defined as a YMRS score of ≥ 16 on any 2 consecutive visits or at the final assessment, or an AE of mania or hypomania.
- Incidence of AEs, discontinuation due to AEs, and serious AEs (SAEs).
- Changes in weight, clinical laboratory tests, vital signs, and ECG measurements.
- Change from baseline in AIMS, BARS, and Modified SAS.
- Frequency and severity of suicidal ideation and suicidal behavior using the C-SSRS.

Document:

Author:

Version Number:
Version Date:

V2.0

21MAY2020

Template No: CS_TP_BS016 Revision 4
Effective Date: 01Apr2016

Reference: CS_WI_BS005

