3.2. METHOD OF ASSIGNING SUBJECTS TO TREATMENT GROUPS

Randomization will be stratified by region. The treatment schedule will be generated by a non-study biostatistician. Once a subject is deemed eligible to be randomized at Day -1, an interactive voice/web-based system (IXRS) will perform the treatment assignment. Subjects will be randomized to 1 of 3 treatments in a 1:1:1 ratio:

- SEP-4199 200 mg/day
- SEP-4199 400 mg/day
- Placebo QD

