3.4. DETERMINATION OF SAMPLE SIZE

A total sample size of 279 evaluable subjects in US and Europe (93 per treatment group: SEP-4199 200 mg/day, SEP-4199 400 mg/day, and placebo) with a global 2-sided alpha of 0.05 will provide about 90% power to reject at least 1 truly significant primary comparison and about 75% power to reject both truly significant primary comparisons using the truncated Hochberg ($\gamma = 0.9$) procedure, assuming treatment effect sizes of 0.44 for both doses of SEP-4199. The effect sizes were selected considering the data from the completed Lurasidone bipolar depression monotherapy study (Loebel 2014). This effect size corresponds to a treatment difference of -3.85 for a SEP-4199 dose with a common standard deviation of 8.745 on the MADRS scale change from baseline at Week 6. An upward adjustment of approximately 5% is used to compensate for information lost due to subjects who are randomized and do not provide any postbaseline primary efficacy data. The total sample size will be approximately 294 randomized subjects (or $N = 98$ subjects per treatment group).

For the secondary efficacy endpoint, assuming the 93 subjects per treatment arm, the study will have 71% power to reject at least one truly significant comparison within the CGI-BP-S family using the regular Hochberg procedure, given a treatment difference of -0.47 for a SEP-4199 dose with a common standard deviation of 1.24 on the CGI-BP-S change from baseline at Week 6. The correlation between the primary and the secondary endpoint is assumed to be 0.8 for each treatment arm.

The sample size was calculated using the Mediana package version 1.05 within R version 3.4.2 ([R Core Team 2017](#))

See [APPENDIX 4](#) for additional power and Type I error rate calculations.

The sample size for the Japanese cohort (45 total [$N = 15$ subjects per group], including 9 dropouts) provides more than 80% probability to have a treatment difference point estimate greater than zero for the MADRS.

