6.6. STATISTICAL TESTS

All statistical inference will be performed with 2-sided tests at the significance level of 0.05 and 2-sided 95% confidence intervals (CIs), unless otherwise specified in the description of the analyses.

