Between group effect size will be defined as: Natural Log(odds ratio)xsqrt(3)/pi

The NNT will be derived as 1/Risk Reduction where Risk Reduction (RR) = (SEP-4199 trt group – placebo response rate). The NNT results will be provided in whole numbers with any fractional values rounded up to the nearest whole number.

The 95% CI will also be presented (only when the lower and upper limits are of the same sign) and are computed by taking the reciprocal of the 95% lower and upper bound of the RR. The lower confidence limit will be rounded down to the largest integer value that is less than the computed estimate, and the upper confidence limit will be rounded up to the smallest integer value that is greater than the computed estimate.

Cochran-Armitage test for trend will be used to test for association between MADRS response and the three treatments.

The log rank testing method will be used to test for differences among the treatments for time to MADRS response. ITT subjects discontinuing the study and those completing the study without meeting the criteria for MADRS response will be censored at the date of last dose of study drug or, if unknown, the end of study date. The analysis will be supplemented with Kaplan-Meier curves to illustrate the differences among the three treatments. A Cox proportional hazards model will also be used with treatment, region, and baseline value as parameters. Wald Chi-square p-value will be included.

A cumulative distribution curve for all treatment groups will be presented, plotting the cumulative percent of MADRS responders versus the percent reduction at Week 6 from baseline.

16.3.3.6. MADRS remission at Week 6

Remission incidence rate, defined as MADRS total score ≤ 12 , will be analyzed similarly to the MADRS responder analysis, including the sensitivity analysis of observed values and of assessing the removal of remote visits (see [Section 16.3.3.5](#)).

Subjects with MADRS total scores ≤ 10 and ≤ 8 at Week 6 will be summarized using descriptive statistics.

A cumulative distribution curve for all treatment groups will be presented, plotting the cumulative percent of MADRS remissions versus the MADRS total score at Week 6.

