PROC LIFETEST OUTSURV=PROBRESPONSE TIMELIST=(9 16 30 44);  
  TIME RSPTIME*RSPSTAT(1);  
  STRATA TRTPN / DIFF=CONTROL ('Placebo');  
RUN;
```

```
ODS OUTPUT HAZARDRATIOS=HAZARDRATIOS PARAMETERESTIMATES=PARAMETERESTIMATES;PROC PHREG;  
  CLASS REGION TRTP (REF='Placebo') / PARAM=REF;  
  MODEL RSPTIME*RSPSTAT(1)=TRTP REGION TOTBL;  
  HAZARDRATIO TRTP / DIFF=REF;  
  CONTRAST '200 MG VS. PLACEBO' TRTP 1 0 / ESTIMATE;  
  CONTRAST '400 MG VS. PLACEBO' TRTP 0 1 / ESTIMATE;  
RUN;
```

Document:

Author:

Version Number:

V2.0

Version Date:

21MAY2020

Template No: CS_TP_BS016 Revision 4
Effective Date: 01Apr2016

Reference: CS_WI_BS005

LOGISTIC REGRESSION

* Placebo is reference;
PROC LOGISTIC DESCENDING;
 CLASS TRTPN REGION / PARAM=REF;
 MODEL RESP = TRTPN REGION TOTBL;
 CONTRAST '200 MG vs. PLACEBO' TRTPN 1 0 / ESTIMATE=EXP;
 CONTRAST '400 MG vs. PLACEBO' TRTPN 0 1 / ESTIMATE=EXP;
 CONTRAST '200 MG vs. 400 MG' TRTPN -1 1 / ESTIMATE=EXP;
CONTRAST '(200 MG + 400 MG) vs Placebo' TRTPN 0.5 0.5 / ESTIMATE=EXP;RUN;

COCHRAN-ARMITAGE TEST

```
PROC FREQ;  
    TABLE TRTP*RESP/CMH TREND;  
RUN;
```

MULTIPLICITY-ADJUSTED P-VALUES

*Example raw p-values;
DATA STUDY;
 INPUT HYP \$ FAMILY PARALLEL \$ SERIAL \$ RAWP;
 DATALINES;
 H1 1 0000 0000 0.1403
 H2 1 0000 0000 0.0095
 H3 2 0000 1000 0.0559
 H4 2 0000 0100 0.0051
 ;
RUN;

%TREEGATE(TEST=HOCHBERG, GAMMA=0.9);

Document:

Author:

Version Number:
Version Date:

V2.0
21MAY2020

Template No: CS_TP_BS016 Revision 4
Effective Date: 01Apr2016

Reference: CS_WI_BS005

PATTERN MIXTURE MODEL (PMM) WITH PLACEBO BASED MI

The steps to implement this sensitivity analysis are as follows. For Japan cohort analysis, code must be adapted by removing REGION variable.

Step 1: Intermittent missing MADRS total scores will be imputed for each treatment using non-missing data from all ITT subjects within the treatment group by a Markov Chain Monte Carlo (MCMC) imputation model which assumes a multivariate normal distribution over all variables included in the imputation model. This imputation is based on the MAR assumption, ie, the missing data are assumed to follow the same model as the other patients in their respective treatment group.

```
PROC MI DATA=xxx OUT=yyy NIMPUTE=1000 SEED=12345 MINIMUM=. . 0 0 0 0 MAXIMUM=. . 60 60 60 60  
MINMAXITER=100;  
    BY TRTP;  
    VAR REGION MADRS_BASE MADRS_Wk1 MADRS_Wk2 MADRS_Wk4 MADRS_Wk6;  
    MCMC CHAIN=MULTIPLE IMPUTE=MONOTONE NBITER=5000 NITER=200;  
RUN;
```

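### The log-rank test for time to MADRS response is not stratified by region, the randomization stratum; stratifying is nearly free and recovers some power if region is prognostic

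*SAP*

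**What the plan says.** SAP 3.2 (and protocol 7.2.1) sets the allocation: "Randomization will be stratified by region". No other stratification factor is named.

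For time to response, SAP 16.3.3.5 says: "The log rank testing method will be used to test for differences among the treatments for time to MADRS response". Protocol 15.3.5.3 specifies the same test, also without strata, and it is the only test of this endpoint there. The code under Time to Response Analysis in SAP Appendix 3 groups PROC LIFETEST by treatment alone, "STRATA TRTPN / DIFF=CONTROL ('Placebo", and a comment directs the programmer to take the raw log-rank p-value from that output.

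SAP 16.3.3.5 then adds a second analysis: "A Cox proportional hazards model will also be used with treatment, region, and baseline value as parameters". It asks for the Wald p-value, and Appendix 3 codes the model as "MODEL RSPTIME*RSPSTAT(1)=TRTP REGION TOTBL".

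Time to response is listed under Other Endpoints (SAP 2.6.4). The two testing families in SAP 7.4 contain only MADRS change and CGI-BP-S depression change at Week 6.

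**The concern.** Region-stratified randomization balances the regions across arms. If region affects how quickly subjects respond, a log-rank test that pools the regions does not use that balance. Its variance is estimated as if region mix could vary freely between arms, and the treatment contrast is diluted by mixing fast and slow responders in one risk set. Both push the test towards non-significance. A region-stratified log-rank compares the arms within region and avoids this.

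At stake is some power for one exploratory endpoint, and a reported p-value that does not follow the design. Two p-values will stand side by side, one unadjusted and one adjusted for region and baseline, with no stated order between them.

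**Working it through.** **The plan's own figure.** The documents state power only for the primary comparisons: "A total sample size of 279 evaluable subjects in US and Europe (93 per treatment group"), about 90% for at least one and about 75% for both. Check: effect size 3.85/8.745 = 0.44; two t-tests sharing placebo; one-sided α = 0.025; truncated Hochberg with γ = 0.9. Both are rejected if the larger p ≤ (γ + (1−γ)/2)α = 0.95α. At least one is rejected if that holds or if the smaller p ≤ (γ/2 + (1−γ)/2)α = α/2. With 400,000 runs this gives 90.2% and 74.7%, against 90.27% and 75.17% in SAP Table 8. That figure reproduces and is untouched by this point. For time to response the documents give no power, event count, hazard ratio or region effect.

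**Inputs from the documents.** 98 randomized per arm; MADRS at days 7, 14, 28 and 42; "All statistical inference will be performed with 2-sided tests at the significance level of 0.05".

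**Assumptions not in the documents.** One dose against placebo; exponential time to response; 40% placebo response by day 42; 15% dropout by day 42; two equal regions balanced across arms; treatment hazard ratio (HR) 1.6 or 1.75; region HR from 1 to 3.

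**What the assumed HRs mean.** With no region effect, a treatment HR of 1.6 moves day-42 response from 40% to 1 − 0.6^1.6 = 55.8%; 1.75 gives 1 − 0.6^1.75 = 59.1%. For region HR r, let x be the non-response probability in the slower region. Then (x + x^r)/2 = 0.6:

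- r = 1.5: x = 0.662, so placebo response is 34% and 46% in the two regions.
- r = 2: x = 0.704, so 30% and 50%.
- r = 3: x = 0.760, so 24% and 56%.

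**Test statistic.** Z = Σ(O − E)/√ΣV. At each visit E = d·n₁/n and V = d·(n₁/n)(1 − n₁/n)(n − d)/(n − 1), with n at risk, n₁ of them on active drug, and d responses. The unstratified test sums over visits with regions pooled. The stratified test computes the terms within each region and sums over visits and regions. Both were applied to the same 4,000 simulated datasets per cell.

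**Power (%), unstratified → stratified**

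| Region HR | Treatment HR 1.6 | Loss | Treatment HR 1.75 | Loss |
|---|---|---|---|---|
| 1 | 58.0 → 57.9 | 0 | 74.5 → 74.4 | 0 |
| 1.25 | 57.9 → 58.3 | 0.4 | 73.8 → 74.4 | 0.6 |
| 1.5 | 57.6 → 58.3 | 0.7 | 73.7 → 74.2 | 0.5 |
| 2 | 55.9 → 58.4 | 2.5 | 72.2 → 74.2 | 2.0 |
| 3 | 52.8 → 59.2 | 6.4 | 68.3 → 73.9 | 5.6 |

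The simulation error of a single entry near 58% is √(0.58 × 0.42/4000) = 0.8 points. Differences are more precise because both tests use the same data.

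**Type I error (treatment HR 1).** Unstratified: 5.3%, 4.9% and 4.2% at region HR 1, 2 and 3. Stratified: 5.5%, 5.5% and 5.6%. The simulation error is √(0.05 × 0.95/4000) = 0.3 points. The unstratified test is not inflated; it drifts below 5% only under a strong region effect.

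**Sensitivity to response rate.** A second simulation at treatment HR 1.6 gave losses at region HR 1.5, 2 and 3 of 1.2, 2.7 and 5.8 points with 40% placebo response (58.0 → 59.2, 54.9 → 57.6, 52.7 → 58.5). With 55% placebo response they were 1.2, 3.3 and 8.6 points (69.1 → 70.3, 65.8 → 69.1, 60.9 → 69.5). At region HR 1 the difference was 0.3 points or less.

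**The case against.** The strongest reply is that the plan already has a region-adjusted test of this endpoint: the Cox model in the same section. Week 6 response is also tested with region in a logistic model. On this view the SAP pairs a simple unadjusted test with an adjusted model, and does the same for responder rate, where the Cochran-Armitage trend test has no region term either. The unstratified log-rank also matches the protocol, and nothing in the documents shows that region predicts response.

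Most of this stands. A reader might infer that region is ignored for time to response, or that this is the one efficacy analysis without it. The Cox model and the Cochran-Armitage test rule out both. A reader might also take a loss of power as established, or expect gains of ten points or more. The documents give no region effect, the loss is zero if there is none, and the largest difference in these runs was 8.6 points, at 55% placebo response and region HR 3.

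What does not stand is that the Cox model settles the matter. It leaves the log-rank p-value unchanged, the SAP says Cox will be used in addition, and no rule says which result leads. Stratifying would not force agreement either: the Cox model also adjusts for baseline MADRS and reports a Wald test.

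**Conclusion.** The point holds as a small, conditional improvement. The log-rank test omits the randomization stratum. It is valid, but mildly conservative if region is strongly prognostic. Under the assumptions listed, stratifying costs essentially nothing when region does not matter. It gains about 1 point or less at region HR 1.5, about 2 to 2.5 points at 2 and about 6 points at 3, and somewhat more if placebo response is higher. A region HR of 3 means placebo response of about 24% against 56%, which would be a large regional difference.

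It would be wrong to infer an inflated error rate or any weakness in the trial's main result. The endpoint is outside the gatekeeping families and has no power claim. Primary and secondary inference, alpha and sample size are unaffected.

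**What to change.** In SAP 16.3.3.5, state that the log-rank comparison of each dose with placebo is stratified by region. In Appendix 3, use `STRATA REGION / GROUP=TRTPN DIFF=CONTROL('Placebo')` for the test. Keep a separate unstratified PROC LIFETEST call for the by-treatment Kaplan-Meier curves and response probabilities, since the present call also supplies those. Drop REGION for the Japan-only analysis, where it is constant. Add one sentence saying whether the log-rank or the Cox p-value leads.

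The cost is one changed line of code, one extra procedure call and two sentences, with no new data. It should be settled before unblinding; a later change would need to be reported as a deviation under SAP section 20.

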Subjects who meet eligibility criteria at Screening will return to the study site on Day -1 for confirmation of screening evaluations as well as completion of predose assessments. Eligible subjects (based on confirmation of study entry criteria) will be randomized and dispensed study drug at Day -1.

Per local clinical practice, subjects may be hospitalized for up to 7 days during the first week of treatment with double-blind study drug. Further need for hospitalization will require consultation with the Medical Monitor.

Subjects will self-administer the study drug on an outpatient basis once daily with or without food beginning on Day 1 (the day after the Baseline visit) and continue for 6 weeks (the last dose of study drug will be self-administered by the subject at home on the morning of Visit 6).

Subjects will be instructed to administer study drug as a single oral dose in the morning at approximately the same time each day. Clinic visits are to begin no later than 6 hours postdose, if possible.

During the baseline (Day -1) and treatment period (Days 1 to 42), subjects will have clinic visits at Days -1, 7, 14, and 28. In order to facilitate scheduling of clinic visits, a window of \pm 2 days will be allowed for each clinic visit. Subjects will have a telephone contact at Day 35 (\pm 2).

End of Treatment (EOT)/Early Termination (ET) (Day 42 [\pm 2])

Subjects will have a clinic visit at Day 42 for assessments of efficacy and safety. Subjects who discontinue the study prior to this visit will undergo the procedures and assessments for this visit at the time of discontinuation.

Follow-up Period (Day 49 [\pm 2])

All subjects who received at least one dose of study drug will have a follow-up visit for safety and tolerability assessments 7 (\pm 2) days after their last study drug dose. Assessment of potential withdrawal effects will also be made during the follow-up period.

Efficacy, Safety, and PK/PD Assessments

Efficacy will be evaluated using the MADRS, CGI-BP-S, and HAM-A. Treatment response and symptom remission will be assessed using the MADRS. Additional assessments will include evaluation of functional impairment associated with bipolar depressive symptoms using the SDS total score and symptom severity using the QIDS-SR16 total score.

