15.3.5.3. Other Efficacy Endpoint Analyses

All other efficacy endpoints will be performed using the ITT population.

The HAM-A and the QIDS-SR16 total scores will be analyzed by the MMRM method described for the primary efficacy endpoint with the appropriate baseline as the covariate.

The HAM-A, the QIDS-SR16, the SDS, and the EQ-5D-5L total scores will be analyzed using an ANCOVA model with treatment, region as fixed effects, and appropriate baseline as a covariate.

A MADRS total score responder is defined as achieving a $\geq 50\%$ reduction from the baseline total score. The MADRS total score responder proportions at Week 6 will be compared among the 3 treatment arms using logistic regression. This model will include treatment and region as fixed effects and baseline MADRS score as a covariate.

The log rank testing method will be used to test for differences among the treatments for time to MADRS responder response. Subjects discontinuing the study and those completing the study without meeting the criteria for MADRS response will be censored at the date of treatment discontinuation or, if unknown, the date of last contact. The analysis will be supplemented with Kaplan-Meier curves to illustrate the differences among the three treatments.

A cumulative distribution curve for all treatment groups will be presented, plotting the cumulative percent of MADRS responders versus the change from baseline in MADRS total score at Week 6.

Remission incidence rates will be analyzed similarly to the MADRS responder analysis.

Details will be provided in the SAP for the other efficacy endpoint analyses and any additional supportive analyses.

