6.5. WINDOWING CONVENTIONS

Apart from early termination data (see [Section 6.3](#)), no visit windowing will be performed during the analysis for this study. Data will be summarized by analysis visit and analyzed by week where applicable (see [Section 6.3](#)).

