LSMESTIMATE TRT01PN*AVISITN "MEAN(200MG+400MG) at Week 2" [1, 1 2] [1, 2 2] / CL divisor=2;  
LSMESTIMATE TRT01PN*AVISITN "MEAN(200MG+400MG) at Week 4" [1, 1 3] [1, 2 3] / CL divisor=2;  
LSMESTIMATE TRT01PN*AVISITN "MEAN(200MG+400MG) at Week 6" [1, 1 4] [1, 2 4] / CL divisor=2;
```

- LS Means Difference estimate (vs Placebo), 95%CI and SE is obtained using following statements:

```
LSMESTIMATE TRT01PN*AVISITN "MEAN(200MG+400MG) vs Placebo at Week 1" [0.5, 1 1] [0.5, 2 1] [-1, 3 1] / CL ;  
LSMESTIMATE TRT01PN*AVISITN "MEAN(200MG+400MG) vs Placebo at Week 2" [0.5, 1 2] [0.5, 2 2] [-1, 3 2] / CL ;  
LSMESTIMATE TRT01PN*AVISITN "MEAN(200MG+400MG) vs Placebo at Week 4" [0.5, 1 3] [0.5, 2 3] [-1, 3 3] / CL ;  
LSMESTIMATE TRT01PN*AVISITN "MEAN(200MG+400MG) vs Placebo at Week 6" [0.5, 1 4] [0.5, 2 4] [-1, 3 4] / CL ;
```

NORMALITY CHECK

```
PROC UNIVARIATE DATA=OUTRESIDUAL NORMAL;  
    VAR STUDENTRESID;  
    VAR PEARSONRESID;  
RUN;
```

ANALYSIS OF COVARIANCE (ANCOVA)

```
PROC MIXED;  
    BY WEEK;  
    CLASS TRTPN REGION;  
    MODEL TOTCFB = TRTPN REGION TOTBL;  
    LSMEANS TRTPN / PDIFF CL;  
RUN;
```

For All SEP-4199 column for safety questionnaires:

- LS Means estimate, 95%CI and SE is obtained using
LSMESTIMATE TRT01AN "MEAN(200 mg,400mg)" 1 1 0 / CL DIVISOR=2;
- LS Means Difference estimate (versus Placebo) , 95%CI and SE is obtained using
ESTIMATE "MEAN(200+400) VS PLACEBO" TRT01AN 0.5 0.5 -1 / CL;

Document:

Author:

Version Number:
Version Date:

V2.0
21MAY2020

Template No: CS_TP_BS016 Revision 4
Effective Date: 01Apr2016

Reference: CS_WI_BS005

MH TEST (FOR SELECTED SAFETY PARAMETERS)

*Conducted for each separate SEP-4199 group versus Placebo;

```
PROC RANK OUT=OUT1 NPLUS1 TIES=MEAN;  
  VAR VSCFB VSBASE;  
  RANKS RKVSCFB RKVSBASE;  
RUN;
```

```
PROC GLM DATA=OUT1;  
  CLASS TRTPN;  
  MODEL RKVSCFB = TRTPN RKVSBASE;  
  OUTPUT OUT=RESIDUAL R=RESID;  
RUN;
```

```
PROC FREQ DATA=RESIDUAL;  
  TABLES TRTAN*RESID / NOPRINT CMH2;  
RUN;
```

For All SEP-4199 column, please select all data and create a new treatment code equal to 1 if subject was treated by SEP-4199 (either 200mg or 400mg) and equal to 0 if he received Placebo. Then use same code as above with this new treatment code.

TIME TO RESPONSE ANALYSIS

* Select Raw Log-rank p-value in SURVDIFF ods dataset;

* Response probability are obtained in PRODUCTLIMITESTIMATES ods dataset;

```
ODS OUTPUT SURVDIFF=SURVDIFF PRODUCTLIMITESTIMATES=PRODUCTLIMITESTIMATES;  

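### Time to MADRS response appears to run on actual days with completers censored inside the Visit 6 window, so the Day 44 Kaplan-Meier estimate overstates cumulative first response by Week 6

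*SAP*

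**What the plan says.** SAP 16.3.3.5 compares time to MADRS response with a log-rank test, a Cox model and Kaplan-Meier curves. Subjects who discontinue or complete without response are "censored at the date of last dose of study drug or, if unknown, the end of study date". Protocol 15.3.5.3 uses different dates: such subjects "will be censored at the date of treatment discontinuation or, if unknown, the date of last contact". SAP 3.7 does not list this among its changes from the protocol.

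The time-to-response code in SAP Appendix 3 runs "PROC LIFETEST OUTSURV=PROBRESPONSE TIMELIST=(9 16 30 44", and a comment there states: "Response probability are obtained in PRODUCTLIMITESTIMATES ods dataset". The variable `RSPTIME` is not defined in words anywhere.

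Three other provisions matter:

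- Protocol 7.1 sets a window of two days either side that "will be allowed for each clinic visit", so Visit 6 may fall on any of Days 40 to 44.
- Protocol 7.1 also says that "the last dose of study drug will be self-administered by the subject at home on the morning of Visit 6". A completer's last-dose date is therefore the date of his or her own Visit 6.
- SAP 6.5 states that, early-termination data aside, "no visit windowing will be performed during the analysis for this study".

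MADRS is rated after baseline only at Weeks 1, 2, 4 and 6 (SAP 16.1.1).

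**The concern.** Response can be seen only at a rating visit. At Visits 3 to 5, a subject without response normally stays in the study and in the risk set, so it does not matter who was seen early in the window. At Visit 6, a completer without response is censored that same day. Someone rated on Day 40 is gone before those due on Days 41 to 44 are rated. Kaplan-Meier then multiplies up to five daily hazards over a shrinking risk set, as if each remaining subject could have been found to respond on every one of those days. In fact each was rated once.

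The result is a reported Day 44 probability, and a final stretch of curve, above the share of subjects who ever responded. The last steps rest on the few subjects seen latest, so the estimate is also less precise. Time to remission is a listed endpoint with no rule or code of its own. It would presumably inherit the same treatment.

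**Working it through.** The plan states no response rate, Kaplan-Meier value or bias, so there is no figure to reproduce.

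**Is the scale actual days?** The reading times 9, 16, 30 and 44 equal 7+2, 14+2, 28+2 and 42+2, the upper ends of the visit windows. They are also the upper bounds of the early-termination mapping for MADRS in SAP 6.3. Nominal time would be read at 7, 14, 28 and 42, or in weeks. With censoring by date as well, actual days is a strong inference, though still an inference.

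**Formula.** Let S30 be the share without response after the Week 4 visit, q the chance of first response at Visit 6 among them, and w_k the share seen on day k of the window. Without dropout:

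- correct survival: S30 × (1 − q)
- Kaplan-Meier at Day 44: S30 × Π_k [1 − q·w_k / Σ_{j≥k} w_j]
- overstatement: the first minus the second

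**One case in full.** Assume S30 = 0.65, q = 0.25 and visits uniform over Days 40 to 44. The daily hazards are 0.25 × (1/5, 1/4, 1/3, 1/2, 1).

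- Product: 0.95 × 0.9375 × 0.9167 × 0.875 × 0.75 = 0.536, where 0.75 is correct.
- Kaplan-Meier response: 1 − 0.65 × 0.536 = 65.2%.
- Correct response: 1 − 0.65 × 0.75 = 51.2%.
- Overstatement: 13.9 points.

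**Spread of visit days** (same S30 and q):

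| Visit 6 days | Overstatement (points) |
|---|---|
| Five days, uniform | 13.9 |
| Five days, weights 1:2:3:2:1 | 16.4 |
| Five days, 60% on Day 42, 10% on each other day | 15.9 |
| Three days, uniform | 9.6 |
| Two days, equal | 6.1 |
| Two days, 10% then 90% | 1.2 |
| One day | 0 |

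Concentration around Day 42 does not help while a few visits fall later, because those few carry the last, largest hazards.

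**Response rate.** First-response percentages at Weeks 1/2/4/6 are assumed, with visits uniform over five days:

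| Assumed pattern | S30 | q | Correct | Kaplan-Meier, Day 44 |
|---|---|---|---|---|
| 4/8/14/14 | 0.74 | 0.189 | 40% | 53.3% |
| 5/10/18/17 | 0.67 | 0.254 | 50% | 64.5% |
| 6/13/22/19 | 0.59 | 0.322 | 60% | 74.2% |

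Over a grid of S30 from 0.55 to 0.85 and q from 0.10 to 0.35, the five-day patterns run from 6.1 to 24.6 points.

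**Subject-level simulation.** This used 93 per arm and SD 8.745 (SAP 3.4), with assumed baseline 30 or 33, mean Week 6 change −10 to −16, correlation 0.6 or 0.75, and 0% or 15% dropout. Uniform visits gave 10.6 to 14.1 points. Peaked or triangular visits gave 14.1 to 15.2. With baseline 30, change −12, correlation 0.6 and no dropout, actual days gave 62.0%, nominal days 48.8% and the truth was 48.8%. Keeping completers without response at risk to Day 44 also gave 48.8%.

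**Precision.** In simulation of the three response patterns (98 per arm, visits spread over five days), the SD of the estimate rose from about 0.05 on nominal weeks to between 0.07 and 0.18 on actual days. Day 30 stayed close to correct.

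**Between-arm comparison.** With assumed changes of −10 and −13.85, the Kaplan-Meier difference was 18.1 points on actual days and 16.9 on nominal days. Log-rank power for 40% against 60% response (93 per arm, 600 trials) was 77.3% on actual and 80.0% on nominal days with uniform visits, and 76.7% and 78.7% with peaked visits. For 40% against 50% the two were within a point.

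**The case against.** The strongest reply is that little depends on this figure. It belongs to an endpoint in the other category, outside the multiplicity scheme. The test is log-rank, and SAP 16.3.3.5 offers the curves as illustration. That stands, and a reader should not infer that the efficacy comparison is at risk: log-rank power moved by under 3 points.

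Second, the time scale is inferred. SAP 6.5 also says data are analysed by week where applicable, so weeks may have been intended. If so, the reading times are wrong for that scale and the definition is still missing.

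Third, a reader might take last-dose censoring as the cause. It is not. Censoring at the Visit 6 MADRS date, which for a completer is the same day, gives the same bias. The cause is actual-day time combined with censoring completers inside the window. The choice between last-dose and last-MADRS dates otherwise moves the estimate by about 1 to 2 points in either direction.

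Fourth, a reader might set the Day 44 figure beside the Week 6 responder table and treat the gap as the error. They are different quantities. Kaplan-Meier estimates first response at any time up to Week 6. The responder table needs response at Week 6 and counts missing as failure (SAP 16.3.1.5). They would differ through transient response and dropout even with correct censoring.

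**Conclusion.** The defect is real. If the plan is followed as it reads, the Day 44 estimate of cumulative first response is biased upward and less precise. The direction follows from the documents once actual-day time is accepted.

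The size does not. It is tempting to quote one narrow figure, such as the 13 to 15 points in the response-rate table, as the error. The documents support no single number, because they give neither a response rate nor a distribution of Visit 6 days. With assumed rates and visits spread over all five days, roughly 10 to 20 points is a fair statement. Wider assumptions give about 1 to 25, and the bias is zero if every Visit 6 falls on one day. Days 9, 16 and 30 are essentially unaffected, and the log-rank comparison is little affected. It should be corrected because a published estimate for listed endpoints would be wrong and the remedy is nearly free.

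**What to change.** In SAP 16.3.3.5 and Appendix 3, define `RSPTIME` in words, and do the same for time to remission, on the analysis-week scale:

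- event at the analysis week (1, 2, 4 or 6) of first response;
- censoring at the analysis week of the last non-missing MADRS, using the existing early-termination mapping in SAP 6.3;
- `TIMELIST=(1 2 4 6)`.

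An alternative that removes this bias equally well is to stay on actual days but keep completers without response at risk through Day 44.

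A discrete-ties option in the Cox model would sit naturally with week-scale data, but it is optional and does not address the Kaplan-Meier bias. No protocol change is needed, since Protocol 15.3.5.3 leaves the details to the SAP. The cost is one derivation rule and one code option, on data already collected.
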